A randomized, double-blind, comparative, effectiveness and safety study of Elevi[®] vs. Hetastarch in subjects undergoing Endoscopic Mucosal Resection (EMR) of colonic lesions equal to or larger than 11mm

NCT03350217

A randomized, double-blind, comparative, effectiveness and safety study of Eleview vs. Hetastarch in subjects undergoing Endoscopic Mucosal Resection (EMR) of colonic lesions equal to or larger than 11mm

Primary Investigator:

[name],
Indiana University Hospital
Indianapolis, IN 46202

Introduction:

EMR is a technique used for the removal of flat or sessile neoplasms confined to the superficial layers of the GI tract using a snare. Injection-assisted EMR is commonly used during resections of larger flat lesions as it provides submucosal lift of polyps, adenomas, other gastrointestinal mucosal lesions or early-stage cancers prior to EMR. This has been found to minimize mechanical or electrocautery damage to the deep layers of the gastrointestinal tract wall as the injectate provides a “safety cushion” as such between the area to be removed and healthy mucosal tissue (ASGE, 2008).

Several solutions are used today for injecting lesions including saline, hyaluronic acid, and hydroxyethyl starch (Hetastarch). Saline solution has been found to dissipate within minutes, which may result in a lower quality lesion lift.

Hyaluronic acid provides a longer lift, but is expensive and is not readily available in the U.S (Hwang, 2015).

A new injectate known as Eleview has been developed for use in gastrointestinal endoscopic procedures and recently approved by the FDA. This injectate boasts a cushion of excellent height and duration through the use of an oil-in-water emulsion. However the initial cost of this material is quite high (\$80 per 10 ml). Hetastarch, which is the current injectate used by [name], is a safe and considerably inexpensive solution that provides prolonged submucosal elevation and lowers procedure times (Fasoulas, 2012). Our study will aim to compare Eleview to Hetastarch in the hopes of finding the ideal submucosal injectate. This trial will focus on polyps of size ≥ 11 mm removed by snare EMR technique. Patients with lesions deemed not suitable for EMR due to features suggestive of sub-mucosal invasion will not be included.

Injectate randomization:

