- Ease of use for polyp removal and fluid behavior combined, and rated on a 5-point scale for: very easy, easy, neutral, difficult and very difficult.
- Time (in minutes) to remove the lesion completely (measured from the first injection to final excision of the lesion), and total time of procedure.
- Need for additional treatments such as avulsion, coagulation or ablation.
- Pathological reports for negative lateral and/or deep margins (lateral margins only accurately assessed in *en bloc* resections)
- Presence and number of deep resections containing muscularis propria.
- *En-bloc* resections histologically examined for free-margins.
- Recurrent or residual neoplasia rates examined by biopsy (if applicable) at the follow-up visit.

Sample size and Statistical Analysis

At least 200 patients will be enrolled. 100 of these patients will be randomized to Elevi[®] injectate and 100 will be given the standard of care, Hetastarch injectate only. Efficacy and safety of Elevi[®] injectate has only been reviewed in one previous study. Therefore, the planned sample size was not calculated using a statistical power analysis, but was regarded as sufficient to repeat the objectives of the COSMO study (2017) and satisfy the exploratory purposes of the present study. Study personnel will carry out a simple randomization using a commonly used online generator. Randomization assignments will then be sealed until day of procedure until patient eligibility has been confirmed. The Principal Investigator will remain blinded and will perform all data analysis after completion of the study.

Data will be summarized and compared using classic descriptive statistics, i.e. mean, standard deviation, coefficient of variation (%), minimum, median and maximum values for quantitative variables, and frequencies for qualitative

variables.

The Sydney Resection Quotient will be compared between treatment groups using a Wilcoxon Rank-Sum test. The proportion of subjects with *en bloc* resection of all endoscopically visible lesions will also be compared between treatment groups using a Fisher's exact test. A nominal alpha level of 0.05 will be used for both the comparisons.

No formal comparison will be performed for the secondary endpoints.

Selection criteria

Inclusion criteria:

1. Sex and age: men and women > 18 years old
2. Subjects referred for EMR of polyps of size ≥ 11 mm
3. ASA score 1, 2 or 3.

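### One 5-point rating covers both ease of polyp removal and fluid behaviour, so an arm difference cannot be attributed to either, and opposite effects can partly or fully cancel

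*Combined protocol and SAP*

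**What the plan says.** In the combined protocol and SAP, the list of secondary endpoints under End-points includes "Ease of use for polyp removal and fluid behavior combined, and rated on a 5-point scale", with the answers "very easy, easy, neutral, difficult and very difficult". The document does not define fluid behaviour, say how the two aspects are to be weighed, provide a separate score for either, or state who completes the rating and when.

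The section on sample size and statistical analysis sets out descriptive summaries: "minimum, median and maximum values for quantitative variables, and frequencies for qualitative" variables. It then states: "No formal comparison will be performed for the secondary endpoints". The sentence "A nominal alpha level of 0.05 will be used for both the comparisons" concerns only the SRQ and the en bloc proportion. On size, "At least 200 patients will be enrolled", 100 per arm.

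Several related quantities are separate secondary endpoints: the volume injected for the first lift and for complete removal, the number of re-injections, the number of pieces, the removal time and the need for additional treatments. The description of Visit 2 says that the endoscopist is kept blind to the injectate.

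**The concern.** This is a double-barrelled item: two questions, one answer. How easily a polyp came away and how the fluid behaved are related but distinct, and a fluid could do better on one than on the other. The merging happens when the box is ticked, so no later analysis can undo it.

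This is the only subjective rating by the operator that the plan lists. The Introduction gives the aim as finding the best submucosal injectate and presents Eleview through its cushion: "This injectate boasts a cushion of excellent height and duration through the use of an oil-in-water emulsion". An operator's view of whether the lift is better, and whether the fluid is easy to work with, bears on that aim. Because the endpoint is not tested, its frequency table is its whole result. A table with similar frequencies in both arms would fit no difference on either aspect, and it would also fit two differences that offset each other. A table favouring one fluid would not show on which aspect it was favoured.

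**Working it through.** The plan states no figure for this endpoint and no effect size or SD, and "the planned sample size was not calculated using a statistical power analysis". There is nothing to reproduce. The check is an argument from the text, followed by an illustration on assumed values.

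**Step 1: what one rating can identify.** Let d1 be the arm difference in ease of removal, d2 the arm difference in fluid behaviour, and w the weight the operator gives to removal. The combined difference is roughly

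w × d1 + (1 − w) × d2.

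One quantity is observed and three are unknown. The plan does not fix w, which may vary from one rating to the next. So d1 and d2 cannot be separated, whatever their signs.

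**Step 2: when the effects cancel.** The expression is zero at w = d2 / (d2 − d1). This lies between 0 and 1 only if d1 and d2 have opposite signs. For d1 = −0.5 and d2 = +0.5, w = 0.5 / 1.0 = 0.5. For d1 = −0.5 and d2 = +0.25, w = 0.25 / 0.75 = 0.33.

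**Step 3: size on a 5-point scale.** Assumed inputs, none from the documents: latent scores for each aspect with SD 1, correlation 0.3 and control mean 3, rounded and limited to 1–5; 200,000 simulated ratings per arm. Taking 1 as very easy, a negative difference means easier than control.

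| d1 (removal) | d2 (fluid) | combined, w = 0.3 | w = 0.5 | w = 0.7 |
|---|---|---|---|---|
| −0.5 | +0.5 | +0.19 | 0.00 | −0.20 |
| −0.5 | +0.25 | +0.02 | −0.12 | −0.27 |
| −0.5 | 0 | −0.15 | −0.25 | −0.35 |
| −0.5 | −0.5 | −0.50 | −0.50 | −0.49 |

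Hand check of the first row: 0.3 × (−0.5) + 0.7 × 0.5 = +0.20; 0.5 × (−0.5) + 0.5 × 0.5 = 0; 0.7 × (−0.5) + 0.3 × 0.5 = −0.20. The simulated values agree to within 0.01. In that row, separate 5-point items would show about −0.48 for removal and +0.48 for the fluid.

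**Step 4: the same opposite effects as frequencies.** Assume a normal latent score with SD 1, control mean 0, and a rating of easy or very easy below −0.5.

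- Removal improved by 0.5: Φ(−0.5 + 0.5) = Φ(0) = 0.500, against Φ(−0.5) = 0.309 in control, so 50% versus 31%.
- Fluid worsened by 0.5: Φ(−0.5 − 0.5) = Φ(−1) = 0.159, against 0.309, so 16% versus 31%.
- An operator who averages the two has a net shift of 0.5 × (−0.5) + 0.5 × 0.5 = 0. With the same spread in both arms, the combined frequencies are identical.

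With 100 per arm and one rating per patient (an assumption), the separate items would show 50 versus 31 and 16 versus 31 patients. The combined item would be expected to show no difference. This is the fully cancelling case; Step 3 gives the range around it.

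**The case against.** The best defence is that the word combined signals a deliberate global rating of ease of use, for which an easy-to-difficult scale is a natural fit. Wanting components is then a design preference. This has some force, and it is why the answer labels are not criticised here. But the text names two components rather than asking for an overall impression, and a global item can sit beside component items.

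Second, both aspects are partly measured elsewhere. A fluid that lifts poorly would be expected to show in volumes or re-injections, and difficult removal in pieces, time or additional treatments. This stands and limits the loss. These measures do not, however, recover the operator's judgement of either aspect.

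Third, nothing in the documents suggests opposite effects. The Introduction praises Eleview's cushion, also credits Hetastarch with lasting elevation, and names only cost against Eleview. A reader might infer that a trade-off between cushion and handling is expected, or that opposite effects always cancel. The documents do not support the first, and the table above contradicts the second: the same ±0.5 effects leave about 0.2 points in either direction at unequal weights, and effects in the same direction do not cancel.

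Fourth, lesion size and site also affect ease of removal. With 1:1 randomisation and a blinded endoscopist, that is noise rather than bias, and it would apply equally to a separate removal item. It is no argument against the combined rating.

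**Conclusion.** The point holds as a minor one. That the two aspects cannot be separated follows from the wording of the item and needs no assumption about the fluids. Cancellation is conditional: it needs effects in opposite directions, and its extent depends on an unstated weighting. The figure of −0.20 to +0.19 for removal weights of 0.7 to 0.3 is an illustration on assumed effects, SD and correlation, not a forecast.

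A reader might go further and infer that the trial risks a false null result, or that its main conclusions are in doubt. The documents do not support that. The item is an untested secondary endpoint, the plan describes the study's purposes as exploratory, and neither the SRQ nor the en bloc comparison nor the sample size depends on it. What is lost is the interpretation of one frequency table.

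**What to change.** Have the blinded operator complete separate 5-point items at the end of the resection, all scored in the same direction:

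1. Ease of polyp removal, very easy to very difficult.
2. Ease of injecting and handling the fluid, very easy to very difficult.
3. Adequacy and persistence of the lift, with its own anchors, for example very good to very poor.

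Three items are needed rather than two. Fluid behaviour may cover both handling and lift, and a single fluid item would merge those again. State in the protocol who rates and when, and report the frequencies of each item by arm. The combined item may be kept alongside as a global rating. If the case report form already scores the components separately, one clarifying sentence in the protocol would be enough.

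The cost is two extra tick-boxes per procedure if the combined item is replaced, three if it is kept, and more descriptive results to report. The sample size and the primary analyses do not change.

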Study patients will be randomly assigned to the Eleview or the Hetastarch treatment group in a 1:1 ratio. Randomization will occur at the site using envelopes provided by the Investigator. The envelopes contents will specify the treatment assignment for each patient and opened by the research team (PI will be blinded).

We will monitor the safety and effectiveness data. The appropriate solutions will be injected into the submucosal space beneath the lesion(s) to be excised before the lesion(s) is/are removed. Subjects in both groups will receive the appropriate volume of injectate deemed necessary by the PI for the individual patient.

Objectives:

Primary objectives of the study are:

- To evaluate the effectiveness of Elevive injection in comparison to Hetastarch, for EMR. Effectiveness will be evaluated by the Sydney Resection Quotient (SRQ), which is defined as the size of the polyp divided by the number of pieces resected.
- To evaluate the safety of Elevive for EMR procedures in relation to adverse events and occurrence of complications during and after the EMR procedure in comparison to Hetastarch injectate.

Secondary objectives:

- To collect other effectiveness data regarding the administration of Elevive in comparison to Hetastarch, such as injectate amount required for efficient lesion lift and complete removal.

End-points:

Primary endpoints:

- Effectiveness of Elevive in comparison to Hetastarch for EMR in terms of:
 - Sydney Resection Quotient
 - Number of subjects with *en bloc* resection of lesions.
- Safety outcomes as assessed by complications during or after the procedures including:
 - Intra-procedural bleeding (bleeding requiring therapeutic intervention during the EMR).
 - Early (<24h) and delayed ($\geq 24h$ post EMR) post-procedural bleeding (bleeding post procedure that necessitates transfusion or endoscopic hemostasis because of hematemesis or a decrease of Hgb concentration of more than 2 g/dL after EMR).
 - Perforation

- Post-Polypectomy Syndrome
- Hospital admissions for any clinically relevant complications post-procedure.

Secondary endpoints:

➤ Effectiveness of Elevi[®] compared to Hetastarch in terms of:

- Injected volume needed for initial lesion lift
- Injected volume needed for complete removal of lesion
- Number of re-injections (number of times the injection device is passed down the scope).
- Number of resected pieces

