During *Visit 2*, inclusion and exclusion criteria will again be confirmed and after the lesion has been measured and found to be ≥ 11 mm and suitable for EMR, the patient will be randomized to the injectate. Polyps will be documented by photographic record prior to randomization. The injectate will be prepared out of sight from the investigator performing the EMR so that the investigator will remain blinded to the injectate. Patient vital signs including BP, HR and SpO2 will be recorded prior to, during, and after the procedure. Once the lesion has been injected, only Boston Scientific Captivator snares measuring 15-20mm will be used to resect the polyps, however additional treatment modalities required will also be recorded.

Visit 3 will consist of a follow up phone call 30 days ± 7 later. The occurrence or persistence of any adverse events will be recorded.

Data integrity and safety:

All paper charts pertaining to the patient will be kept under lock and key in coordinators office away from the endoscopy area. The data entry will be performed into an excel file which will be stored on an internal network drive with encryption and password security. Regular quality control checks of the data will be performed. Only approved personnel by the IRB will have access to the file storage. This file will also not have any identifiable information (name, DOB or

mrn). A study log with the identifiable information will be kept in a separate folder (also encrypted) to enable the investigators to assist in any research audit. No procedural data except the date of examination will be entered into this log. The data and safety will reviewed annually in addition to the continuous PI monitoring. Protocol revisions will be proposed, if needed, based on the results of the safety review including, but not limited to, stopping the randomization process.

References:

COSMO (2017). A randomized, double-blind, comparative, effectiveness and safety study of SIC 8000 in subjects undergoing Endoscopic Mucosal Resection (EMR) of colonic lesions equal to or larger than 2 cm

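### The sample size is justified by a study of lesions of 2 cm or more, but the plan enrols from 11 mm and gives no SRQ result for lesions of 2 cm or more

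*Combined protocol and SAP*

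**What the plan says.** Under Sample size and Statistical Analysis the plan states "At least 200 patients will be enrolled", 100 per arm, and says openly that "the planned sample size was not calculated using a statistical power analysis". Two grounds are offered instead: the number "was regarded as sufficient to repeat the objectives of the COSMO study (2017) and satisfy the exploratory purposes of the present study".

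The documents describe COSMO only through its title in the References, a study "in subjects undergoing Endoscopic Mucosal Resection (EMR) of colonic lesions equal to or larger than 2 cm". Inclusion criterion 2 of this trial reads "Subjects referred for EMR of polyps of size ≥ 11 mm". The title, the Introduction, the excluded-lesion list and the Visit 2 description all use the same 11 mm threshold.

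The first primary effectiveness endpoint is SRQ, "which is defined as the size of the polyp divided by the number of pieces resected". It is compared between arms with one Wilcoxon rank-sum test at a nominal 0.05. En bloc resection is the second, tested by Fisher's exact test at the same level. Randomisation is simple. The plan has no size stratum, no minimum number of lesions of 2 cm or more, and no size-specific or size-adjusted analysis. Under Visit 2, the lesion is measured before the patient is randomised.

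**The concern.** The sufficiency remark is borrowed from one population and applied to a wider one, and the endpoint does not behave alike in the two. A lesion removed in one piece has an SRQ equal to its own size, whichever fluid was used. The plan prescribes 15-20 mm snares, so many lesions of 11-19 mm could come out whole in either arm. In those patients SRQ would largely report polyp size. The fluid has most room to change SRQ where removal is piecemeal, which is more likely in the COSMO range.

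The pooled comparison therefore depends on how many large lesions happen to be referred, and the plan neither sets nor predicts that share. What is at stake is interpretation. The Introduction contrasts a product at $80 per 10 ml with an inexpensive comparator. A null pooled SRQ could be taken as a failure to repeat COSMO, or as evidence that the fluids are equivalent in large lesions, when no estimate for large lesions was planned.

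**Working it through.** **1. The plan's own figure.** The 200 cannot be reproduced, because no effect size, SD, power or dropout is given. What can be computed is the standardised difference that 100 per arm detects (two-sided 0.05, assumed because sidedness is not stated):

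- d = (1.960 + 0.842) × √(2/100) = 0.396 at 80% power.
- With Wilcoxon efficiency 3/π: 0.396 / √(3/π) = 0.405.

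**2. Dilution by simple arithmetic.** Assume an effect of D standard deviations in lesions of 2 cm or more, none in smaller ones, and a share f of patients with large lesions. The pooled effect is D × f. Pooled power is Φ(D·f·√(100·(3/π)/2) − 1.960). For the large-lesion subset, use D and 100·f per arm.

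At D = 0.5:

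- f = 1: 0.5 × 6.910 − 1.960 = 1.495, power 93%.
- f = 0.5, pooled: 0.25 × 6.910 − 1.960 = −0.233, power 41%.
- f = 0.5, subset of 50 per arm: 0.5 × 4.886 − 1.960 = 0.483, power 69%.

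Pooled power for other values:

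| D | f = 100% | 75% | 50% | 25% |
|---|---|---|---|---|
| 0.4 | 79% | 55% | 28% | 10% |
| 0.5 | 93% | 74% | 41% | 14% |
| 0.6 | 99% | 88% | 55% | 18% |

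At f = 0.5 the effect needed within large lesions for 80% pooled power doubles, to 0.405/0.5 = 0.81 SD.

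**3. Simulation with SRQ itself.** Every input except the 100 per arm and the test is an assumption. Large lesions are 20-45 mm, with 1 + Poisson(size/9) pieces and a floor of two; the Poisson mean is 25% lower on Eleview. Lesions of 11-19 mm take one piece or two. Power is given as pooled / subset of 20 mm or more:

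| One-piece rate in small lesions, Eleview vs Hetastarch | 100% large | 70% | 50% | 30% |
|---|---|---|---|---|
| 90% vs 90% | 92% | 52% / 80% | 26% / 65% | 11% / 45% |
| 90% vs 80% | – | – | 47% / 66% | – |
| 90% vs 70% | – | – | 74% / 67% | 69% / 40% |

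Repeat runs agreed to within about four percentage points. In the first row the mean SRQ difference is 1.75 with all lesions large and 0.89 at a 50% share. The 1.75 depends on the two-piece floor; without it the difference is about 2.36.

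**4. A different piece-count model.** Here pieces are 1 + Poisson(k × (size − 15)/10) for sizes above 15 mm, with k = 1.5 against 1.1. Pooled power at shares of 100 / 75 / 50 / 25% is 88 / 64 / 36 / 13% if only large lesions benefit. It is 88 / 70 / 48 / 25% if the same relative effect applies at every size.

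**Reading.** When the fluid acts only in large lesions, or has the same relative effect at every size, pooled power falls as the share of small lesions rises. When it strongly raises one-piece removal of small lesions, pooled power holds up much better and the pooled test beats the subset test.

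**The case against.** The case for the plan is substantial. It disclaims any power calculation and calls its purpose exploratory, so wider entry falsifies no power claim. Repeating COSMO's objectives need not mean repeating its population. The 11 mm threshold is in the title and is deliberate. If the average effect in that population is smaller, that is the true answer to the question asked, not a bias. En bloc resection is a second primary test, and it can pick up an effect on one-piece removal. Nothing in the documents says that 11-19 mm lesions usually come out whole or that the fluid cannot change this; lesions of 16-19 mm exceed the smallest permitted snare.

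All of that stands, and it rules out two stronger readings. A reader might infer that the trial is underpowered or that entry from 11 mm is a mistake; the documents support neither. A reader might also infer that a test in lesions of 20 mm or more is simply the better test. The 90% against 70% row shows the reverse, so that advantage depends on the assumed effect in small lesions.

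One point is left unanswered. The plan does invoke COSMO as a ground for its number, and following the plan as written yields no SRQ estimate in the size range that COSMO's title names. The en bloc test is also pooled over size, so it does not fill that gap.

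**Conclusion.** The point holds as a mismatch between justification and read-out, with a cheap improvement available. It is not a design error. The COSMO-based sufficiency remark does not carry over unchanged to a population starting at 11 mm, and the pooled SRQ result alone cannot settle the question for lesions of 2 cm or more.

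The size of the consequence is uncertain. At a 50% share of large lesions, pooled against subset power ranged from 26% against 65% to 74% against 67%, depending on the assumed effect in small lesions. The documents give no expected size mix, SRQ effect, SD or piece counts. In the simple calculation the loss is modest if about three quarters of lesions are large and the effect is around 0.6 SD (99% to 88%). It is severe if large lesions are a minority and small ones do not respond.

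**What to change.** 1. Keep entry at 11 mm and the primary SRQ comparison in all patients. Prespecify the SRQ difference (Hodges-Lehmann with 95% CI) separately for patients whose largest lesion measured before randomisation is 11-19 mm and 20 mm or more. Label these as supportive estimates, not a third confirmatory test at 0.05. State that no conclusion of equal performance in large lesions will be drawn from the pooled SRQ alone.
2. Prepare two envelope sets, one per size band, each in permuted blocks; simple randomisation within each set would not balance the arms. Account for the stratum in the primary SRQ comparison, for example with a van Elteren test. Size is already known before the envelope is opened, so the workflow does not change.
3. Reword the sufficiency sentence to say that COSMO concerned lesions of 2 cm or more and that only patients with a lesion of 20 mm or more correspond to that population.

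Cost: protocol wording, one extra analysis of data already collected, and a blocked two-set envelope list. No patients or procedures are added. The change should be made before outcome data are seen, since a later split by size would be post hoc. The downside is precision. At a 50% share the large-lesion estimate rests on about 50 per arm, so its interval is roughly √(100/50) = 1.4 times as wide as with 100 per arm. The fix also does not guarantee any number of large lesions; that still depends on referral.

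### Lesion size is known before randomisation and plausibly predicts en bloc resection, but the planned en bloc test ignores it: the test is valid, yet may give up some precision and leaves a chance size imbalance uncorrected

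*Combined protocol and SAP*

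**What the plan says.** The section on sample size and statistical analysis names two formal tests, each at a nominal 0.05, and neither uses a covariate:

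- En bloc: the proportion of subjects with "resection of all endoscopically visible lesions will also be compared between treatment groups", by Fisher's exact test.
- SRQ: "The Sydney Resection Quotient will be compared between treatment groups using a Wilcoxon Rank-Sum test". SRQ itself is "defined as the size of the polyp divided by the number of pieces resected" (primary objectives).

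On allocation, "Study personnel will carry out a simple randomization using a commonly used online generator"; no stratification is mentioned. On size of trial, at least 200 patients are planned, 100 per arm, and "the planned sample size was not calculated using a statistical power analysis". Otherwise, "Data will be summarized and compared using classic descriptive statistics" and "No formal comparison will be performed for the secondary endpoints".

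The inclusion criteria admit "Subjects referred for EMR of polyps of size ≥ 11 mm", and no upper size limit appears. The Visit 2 description has the lesion measured and photographed before the patient is randomised, and limits resection to snares of 15-20 mm.

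**The concern.** Size fixed before allocation cannot be affected by the injectate, so it is a legitimate baseline covariate. A lesion wider than the largest permitted snare is plausibly harder to remove in one piece, so size may explain a good part of the variation in en bloc resection. An unadjusted comparison leaves that variation in the error term.

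Simple randomisation also lets the arms differ in size mix by chance. Part of an observed en bloc difference would then reflect size, and no planned analysis separates the two:

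- Descriptive summaries can show an imbalance but not correct for it.
- The number of pieces is a secondary endpoint and gets no formal test.
- Having size in the SRQ numerator is not adjustment. When a lesion comes out in one piece, SRQ simply equals its size.

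The sample size rests on no power calculation, so there is no known margin of precision to spare.

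**Working it through.** **Figure to reproduce.** None. The 200 patients have no formula or design inputs behind them.

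**Inputs from the plan.** 100 patients per arm; simple randomisation; alpha 0.05 (sidedness is not stated; two-sided taken here); size 11 mm or more, measured before randomisation.

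**Assumed, because the documents give no such figures.** The share *s* of patients with lesions up to 20 mm (30% or 50%); control en bloc rates in the two size groups, differing by a gap *g*; a common treatment odds ratio of 1.75 or 2.25; one outcome per patient.

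**Step 1: how often the arms differ in size mix.** The difference between arms in the share up to 20 mm has SD = √(s(1−s)·2/100).

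- s = 0.5: √(0.25 × 0.02) = 0.0707. P(difference of at least 10 points) = 2[1 − Φ(0.10/0.0707)] = 15.7%.
- s = 0.3: √(0.21 × 0.02) = 0.0648. The same probability is 12.3%.

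**Step 2: what such an imbalance does.** The crude en bloc difference shifts by imbalance × gap. A 10-point imbalance gives 0.10 × 20 = 2 points, 0.10 × 40 = 4 points or 0.10 × 50 = 5 points. With an overall rate of 50%, the standard error of the difference is √(2 × 0.25/100) = 7.1 points.

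**Step 3: variance explained by the two size groups.** The fraction is s(1−s)g²/[p̄(1−p̄)], where p̄ is the overall control rate. At s = 0.5:

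- .60/.40: 0.25 × 0.04/0.25 = 4%
- .70/.40: 0.25 × 0.09/0.2475 = 9%
- .70/.30: 0.25 × 0.16/0.25 = 16%
- .75/.25: 0.25 × 0.25/0.25 = 25%

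**Step 4: one power comparison by hand.** Take control rates .70/.30, s = 0.5 and odds ratio 2.25.

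- Treated rates: odds 2.333 × 2.25 = 5.25, so .840; odds 0.4286 × 2.25 = 0.964, so .491.
- Overall: .665 against .500, a difference of .1655.
- Unadjusted: pooled rate .583, SE = √(.2432 × .02) = .0697, z = 2.37, power = Φ(2.37 − 1.96) = 66%.
- Stratified: pooled rates .770 and .395, mean within-group variance (.1771 + .2391)/2 = .2081, SE = √(.2081 × .02) = .0645, z = 2.56, power = Φ(2.56 − 1.96) = 73%.
- Gain: about 7 points.

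**Step 5: simulation over the grid.** CMH is compared with the unadjusted chi-square test, both without continuity correction. The benchmark is not Fisher's test, because Fisher's conservatism would inflate the apparent gain. Ranges cover repeated runs with 20,000 trials per cell; a further run with 200,000 per cell agrees.

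| Control en bloc rate, ≤20 / >20 mm | Gap (points) | Power, CMH minus chi-square (points) |
|---|---|---|
| .50/.50 | 0 | about −0.6 to 0 |
| .60/.40 | 20 | about 0 to 1 |
| .70/.40 | 30 | 2 to 4 |
| .70/.30 | 40 | 3 to 7 |
| .75/.25 | 50 | 6 to 12 |

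In null trials where the arms differ by at least 10 points in the share up to 20 mm, the unadjusted test rejects in about 9-13% at gaps of 40-50 points, against about 5% for CMH. Over all null trials both tests are at about their nominal level.

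**Step 6: other models.**

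- *Size generating the number of pieces, one lesion per patient.* The gain is −0.8 to 3.4 points in four weak or moderate models (simulation error about 1 point) and 3.7 to 9.1 in two steep ones.
- *Several lesions in 30% of patients, largest lesion as covariate.* The gain is 0.4 to 4.0 and 3.9 to 8.0 points respectively.
- *Cut-point.* In one steep model, unadjusted power of .314 becomes .346, .404 and .412 with cuts at 15, 20 and 25 mm. In a moderate one, .349 becomes .364, .377 and .384. The result does not hinge on 20 mm.
- *Logistic model in continuous size.* Adjustment cuts the variance of the en bloc difference by about 2%, 15% and 25% for odds ratios of 1.5, 2.5 and 4 per SD of size.

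**The case against.** The strongest reply is that nothing is wrong. Unadjusted comparison of randomised arms is accepted practice, the study describes itself as exploratory, and the plan pre-specifies two standard tests. The benefit rests on an association that the documents never quantify; the snare rule is the only support. Where size is weakly prognostic, CMH at 20 mm gains nothing detectable, and a gain of 1-3 points would rarely change a conclusion. All of this stands, and it is why the point is of low severity.

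Three stronger readings are tempting and are not supported:

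- A reader might infer that the planned tests are biased, or that the trial's false-positive rate is 9-13%. It is not. Those figures apply only to trials selected for imbalance, and only if size is strongly prognostic.
- A reader might infer that the SRQ analysis must change as well. Simulated gains from size-adjusted rank analysis of covariance were 0.1-5.0 points in the weak and moderate models and larger only at the extremes. The direction of the relation between size and SRQ is unknown. While the Wilcoxon test remains primary, none of that gain reaches the primary SRQ result.
- A reader might infer that every eligible lesion already has a size recorded before allocation. The Visit 2 text speaks of one lesion being measured, while the en bloc endpoint covers all visible lesions. Patient-level size therefore has to be defined.

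**Conclusion.** The point holds as a low-severity efficiency improvement for the en bloc comparison, not as a validity failure. Size is available before randomisation, plausibly prognostic and unused, and nothing else in the plan corrects a chance imbalance in it.

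The worth of adjustment depends on a quantity that the documents do not give. It is negligible if en bloc rates differ by 20 points or less across 20 mm, a few points of power at 30-40, and 6-12 points at 50. The downside is up to about 0.6 points if size does not matter. These figures assume 200 patients, simple randomisation, 30-50% of patients with lesions up to 20 mm, and a treatment odds ratio that is the same in both size groups.

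**What to change.** In the section on sample size and statistical analysis:

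1. Make the en bloc comparison a single CMH test, two-sided at 0.05 without continuity correction, stratified by pre-randomisation lesion size (≤20 mm, >20 mm). Name this one method rather than offering alternatives.
2. Keep Fisher's exact test as a sensitivity analysis, and report en bloc proportions by arm, overall and within each size group.
3. Define patient-level size as the largest eligible lesion measured before the envelope is opened, and record that value.
4. Leave the Wilcoxon test as the SRQ analysis. A size-adjusted SRQ analysis is optional; if included, label it supportive.

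The randomisation need not change. The cost is a few sentences, one data field, slightly more analysis work and the small power loss above if size proves irrelevant. For patients with several lesions, the team must note before allocation which lesions have been found and which is largest; the current text does not establish that this is already done. The change should be made before the randomised groups are compared, because an adjustment added after an imbalance is seen would look data-driven.
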